5.5.1. Objective Response rate (ORR)

Primary Analysis in Part B – ORR by ICR

The following analyses will be performed.

The best overall response will be tabulated, and ORR with 95% CI will be calculated using the Clopper-Pearson method. Confirmed and unconfirmed responses will be listed.

- For Part B, 2-sided 90% CI will also be provided.
- Waterfall plot of target lesion will be provided.

Secondary Analysis in Part A, B – ORR by investigator

The following analyses will be performed.

- The best overall response will be tabulated, and ORR with 95% CI will be calculated using the Clopper-Pearson method.
- Waterfall plot of target lesion will be provided.

5.5.2. Disease Control Rate (DCR)

Secondary Analysis in Part A & B – DCR by investigator

The following analyses will be performed.

- The best overall response will be tabulated, and DCR with 95% CI will be calculated using the Clopper-Pearson method.

5.5.3. Duration of Response (DoR)

Both DoR by ICR and DoR by investigator will be performed. [Table 5](#) summarizes event and censoring rules for DoR.

Table 5: Event and Censoring Rules for DoR

Event/Censor	Decision	Date of event or censor to consider for analysis
Documented first disease progression	Event	Date of 1 st PD scan
Death without disease progression	Event	Date of Death
Patients who not known to have progressed or died at the time of data cut-off	Censor	Date of last evaluable tumor scan (non-NE)
Patient progresses or dies immediately after two or more consecutive missed visits	Censor	Date of last evaluable tumor assessment prior to the two missed visits (non-NE)

For missing data, i.e., patients who were lost to follow-up or who have withdrawn their consent without radiological progression or reached the time point of analysis without a known record of death or disease progression, the DoR will be censored at the date of last evaluable tumor scan.

Secondary Analysis in Part A & B – DoR by investigator

The following analyses will be performed.

- The Kaplan-Meier method will be used to estimate the median and percentile with the 2-sided 95% CI calculated using the Brookmeyer and Crowley method.
- Swimmer plot of treatment duration and response will be provided.

Secondary Analysis in Part B – DoR by ICR

The following analyses will be performed.

- The Kaplan-Meier method will be used to estimate the median and percentile with the 2-sided 95% CI calculated using the Brookmeyer and Crowley method.
- Swimmer plot of treatment duration and response will be provided.

5.5.4. Intracranial ORR (icORR)

Both icORR by ICR and icORR by investigator will be performed.

Secondary Analysis in Part A & B – icORR by investigator

The following analyses will be performed.

- The best overall response in the CNS will be tabulated, and icORR with 95% CI will be calculated using the Clopper-Pearson method.
- Waterfall plot of target lesion will be provided.

Secondary Analysis in Part B – icORR by ICR

The following analyses will be performed.

- The best overall response in the CNS will be tabulated, and icORR with 95% CI will be calculated using the Clopper-Pearson method.
- Waterfall plot of target lesion will be provided.

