5.2. Exclusion Criteria

A patient must not meet any of the following exclusion criteria to be eligible for participation in this study:

1. Currently receiving an investigational drug in a clinical trial or participating in any other type of medical research judged not to be scientifically or medically compatible with this study
2. Has received prior treatment with any of the following within the specific time frame prior to the first dose of study treatment:
 - a. Major surgery/surgical therapy for any cause within 4 weeks; the patient must have recovered adequately from the toxicity and/or complications of the intervention prior to starting study treatment
 - b. Chemotherapy, biologic therapy, targeted therapy, immunotherapy, or investigational agents within 5 half-lives or within 4 weeks (whichever is shorter) prior to the first dose of study treatment. Patient must have recovered from toxicities of the prior therapy based on the Investigator's judgement prior to starting study treatment
 - c. No prior treatment with:
 - (i). **Part A1** (Phase 1 Dose Escalation): Systemic immunotherapy (eg, PD-1/PD-L1 antibody)
 - (ii). **Parts A2, B, and C**: Any EGFR C797S mutation-targeting agent (eg, BLU-945)
 - d. Radiotherapy prior to the start of study treatment within:
 - (i). 2 weeks for radiation therapy of non-thoracic regions (7 days for palliative radiation of single lesions)
 - (ii). 3 months for radiation therapy including thoracic region.

Patients must have recovered from all radiation-related toxicities, not require corticosteroids, and not have had radiation pneumonitis.
3. Have any unresolved clinically relevant toxicity of Grade ≥ 2 from previous anti-cancer treatment, except for alopecia, skin pigmentation, and Grade 2 prior platinum-therapy related neuropathy. Patients with chronic, but stable Grade 2 toxicities may be allowed to enroll if the Investigator and Sponsor agree.

4. Any strong and moderate inhibitors/inducers of cytochrome P450 (CYP) 3A two weeks prior to start of therapy. If a patient is receiving strong inhibitors/inducers of CYP3A (see [Appendix A](#)), these medications and substances must be discontinued ≥ 2 weeks prior to the first dose of study treatment.
5. Has the following CNS metastases disease status:

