 - a. **Part A1** (Phase 1 Dose Escalation): Known untreated central nervous system (CNS) metastases, or history of uncontrolled seizures, or leptomeningeal disease. Patients with treated brain metastases are eligible if there is no evidence of progression for at least 4 weeks after CNS-directed treatment, as ascertained by clinical examination and brain imaging (MRI or CT scan) during the screening period, and they are on a stable or decreasing dose of corticosteroids for at least 2 weeks prior to the first dose of study treatment.
 - b. **Parts A2, B, and C**: Spinal cord compression, symptomatic and unstable CNS metastases, requiring steroids over the last 4 weeks prior to enrollment (asymptomatic and symptomatic brain metastases stable for at least 4 weeks and off steroids are allowed). Patients with leptomeningeal disease are allowed if it is determined that immediate CNS treatment is unlikely to be required.
6. Impaired cardiac function or clinically significant cardiac disease, including any of the following:
 - a. Baseline QT interval > 470 msec corrected for heart rate using Fridericia's formula (QTcF, verified on repeat measurements)
 - b. History of QTc prolongation or predisposition for QTc prolongation (clinically relevant electrolyte abnormalities, cardiac disorder, bradycardia, etc.), or family history of sudden cardiac death or QT prolongation (long QT syndrome)
 - c. Regular use of medications known to prolong QTc interval or to be arrhythmogenic (such as ondansetron, erythromycin, droperidol) within 2 weeks of the first dose of TAS3351. A list of these medications can be found at: <http://crediblemeds.org>.
 - d. History or presence of clinically important abnormalities in rhythm or conduction in resting ECG (eg, sinus arrest, second- or third-degree atrioventricular block (first degree atrioventricular block not excluded), serious uncontrolled ventricular arrhythmias), or severe myocardial infarction within 6 months of screening.
7. General health condition of the patient is not suitable for the study including:
 - a. Disease or condition that significantly affects gastrointestinal absorption of the study treatment
 - b. Clinically relevant active infection (ie, known HBV, HCV, HIV – screening not required) or other uncontrolled medical condition
 - c. History of interstitial lung disease/pneumonitis, drug-induced lung disease/pneumonitis

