9.2. Efficacy Endpoints

Efficacy endpoints based on radiographic imaging will be assessed per RECIST 1.1; endpoint definitions are summarized in [Table 15](#).

Table 15: Efficacy Endpoint Definitions

Endpoint	Definition
ORR	Proportion of patients experiencing a best overall response of PR or CR (per RECIST v1.1). Intracranial ORR be assessed based on ORR of CNS lesions only
DoR	Time from the first documentation of response to the first documentation of objective tumor progression or death due to any cause, whichever occurs first. Intracranial DoR be assessed based on DoR of CNS lesions only
DCR	Percentage of patients who have achieved a CR, PR, or stable disease (SD)
PFS	Time from date of first dose to the date of documentation of disease progression, or date of death, whichever occurs first
OS	Measured from the date of first dose until the date of death due to any cause

Abbreviations: CNS=central nerve system; CR=complete response; DCR=disease control rate; DoR=duration of response; ICR=independent central review; ORR=objective response rate; OS=overall survival; PFS=progression-free survival; PR=partial response; RECIST=Response Evaluation Criteria in Solid Tumors; SD=stable disease

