5.3.3. Baseline Disease Characteristics

The following nature and duration of cancer will be summarized. Listings will also be provided.

- Time since initial diagnosis (years)
= (Year of informed consent) – (Year of initial diagnosis) + 1
- Age at initial diagnosis
= (Age at the time of informed consent) – (Time since initial diagnosis)
- Time since confirmation of first metastasis (years)
= (Year of informed consent) – (Year of the first metastasis confirmed) + 1
- Cancer stage (TNM: I A1 to IV B) at the time of initial diagnosis
- Histology (Adenocarcinoma/Squamous cell carcinoma/Neuroendocrine tumors/Large cell carcinoma/Other)
- Grade of tumor (Well differentiated/Moderately differentiated/Poorly differentiated/Undifferentiated/Unknown)
- Presence and absence of CNS metastases
- New CNS metastases (yes/no)
- CNS metastases progressing after last treatment (yes/no)
- Patient with leptomeningeal disease (yes/no)
- Results of local tumor tissue/cfDNA analysis
 - Type of sample (Tumor tissue, cfDNA from blood sample)
 - Assay method (NGS, PCR, Other)
 - Type of EGFRmt (C797S/ Exon 19 Deletion/ Exon 20 insertion/ E709X/ G719X/ L858R/ L861Q/ L861R/ S768I/ T790M/ Amplification/ Other)

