5.5. Efficacy Analyses

Unless otherwise specified, all efficacy analyses will be performed based on all treated population. The definition for confirmation and duration of overall response is presented in the protocol Appendix C.

The description of each efficacy endpoint is provided in [Table 4](#).

Table 4: Efficacy Endpoint Definitions

Endpoint	Definition
ORR	The proportion of patients experiencing a best overall response of PR or CR (per RECIST 1.1), based on IRC (and Investigator assessment). (investigator assessment only for part A)
DCR	The proportion of patients experiencing a best overall response of SD, PR, or CR (per RECIST 1.1), based on IRC (and Investigator assessment) (investigator assessment only for A)
DoR	For patients who demonstrated CR or PR as the best overall response, the time from the first documentation of response as CR or PR (per RECIST 1.1 based on IRC and Investigator assessment; investigator assessment only for part A to the first documentation of objective tumor progression or death due to any cause, whichever occurs first. If a patient does not progress or die following a response, then their DoR will use the PFS censoring time. - (Date of PD/death or censoring) – (date of first response of CR/PR(as BOR)) + 1.
PFS (All treated)	Time from date of first dose to the date of documentation of disease progression, or date of death, whichever occurs first - (Date of PD/death or censoring) – (date of first dose) + 1.
OS (All treated)	Measured from the date of first dose until the date of death due to any cause - (Date of death or censoring) – (date of first dose) + 1.

The best overall response (BOR) is determined once all the data for the patient, which are assessments obtained after study treatment discontinuation or starting a subsequent anti-cancer therapy, are known. The following best overall responses are defined based on the timepoint level response.

- Complete Response (CR): Required two timepoint assessments of CR, with the second at least 4 weeks after the initial CR. An intervening timepoint assessment of PR, SD, or PD will not be confirmed as CR.
- Partial Response (PR): Required a first assessment of PR and a second assessment of PR (or CR) at least 4 weeks after the initial PR. An intervening timepoint assessment of SD or PD will not be confirmed as PR.

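### Intracranial response is not split by prior local CNS treatment, so responses in treated, non-progressing brain metastases cannot be attributed to TAS3351 alone

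*SAP*

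**What the plan says.** **Endpoint.** Protocol 9.2, Table 15: "Intracranial ORR be assessed based on ORR of CNS lesions only". The same section states: "Efficacy endpoints based on radiographic imaging will be assessed per RECIST 1.1". SAP 5.5.4 repeats the tabulation for Part A and Part B by investigator and for Part B by ICR: "The best overall response in the CNS will be tabulated, and icORR with 95% CI will be calculated using the Clopper-Pearson method". SAP 5.5.5 does the same for icDoR, using the DoR event and censoring rules. The default efficacy population is in SAP 5.5: "Unless otherwise specified, all efficacy analyses will be performed based on all treated population".

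**Eligibility (Protocol 5.2).** Part A1 excludes known untreated CNS metastases and then says: "Patients with treated brain metastases are eligible if there is no evidence of progression for at least 4 weeks after CNS-directed treatment". For Parts A2, B and C: "asymptomatic and symptomatic brain metastases stable for at least 4 weeks and off steroids are allowed". The radiotherapy washout in exclusion 2d is "2 weeks for radiation therapy of non-thoracic regions (7 days for palliative radiation of single lesions"; the patient must also have recovered from radiation toxicity and not need corticosteroids.

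**Baseline data.** SAP 5.3.3 summarises whether CNS metastases are new and, separately, "CNS metastases progressing after last treatment (yes/no". SAP 5.3.5 summarises radiotherapy intent and whether the field was thoracic, and lists all collected prior surgery and radiotherapy data. No efficacy analysis refers to any of these variables.

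**The concern.** A brain lesion treated locally before its baseline scan may go on shrinking afterwards. If it does so on study, the CNS best overall response can become PR or CR whether or not the drug reached the lesion, and the patient then contributes an icDoR as well. There is no control arm, so the only protection is to state which lesions count, or to report the two kinds of patient apart. The plan does neither.

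Brain penetration is part of the stated rationale for TAS3351 (Protocol 2.1.2), and icORR and icDoR are secondary endpoints in Parts B and C. Protocol 4.2.2 allows a brain-metastasis cohort to be added by amendment if Part A looks promising. Part A1 is where the difficulty is sharpest, because eligibility there leaves few known lesions of any other kind.

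The protocol already treats irradiation of measurable disease as a confounder on study: under 6.4.3 such a patient is censored for the primary efficacy analysis. There is no counterpart for irradiation before baseline.

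**Working it through.** **1. Endpoint against eligibility, part by part.**

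| Part | Known CNS lesions that may be present at baseline | icORR assessed by | Condition on prior local treatment |
|---|---|---|---|
| A1 | Treated, no progression for at least 4 weeks after CNS-directed treatment | Investigator (SAP 5.5.4) | None stated |
| A2 | Stable at least 4 weeks and off steroids, treated or not | Investigator (SAP 5.5.4) | None stated |
| B | As A2 | ICR and investigator | None stated; Site Imaging Manual not supplied |
| C | As A2 | ICR and investigator (Protocol 3.3) | None in Table 15; this SAP covers only Parts A and B |

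**2. Timing in Parts A2, B and C.** The washout and the stability condition apply together. The 4 weeks run on stability and are not tied to the date of CNS treatment. As written, a lesion irradiated between 2 and 4 weeks before first dose (from 7 days if a palliated single lesion) and stable throughout is not excluded.

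**3. Whether anything later separates the two effects.** Confirmation of CR or PR at least 4 weeks later (SAP 5.5) does not: a continuing radiation effect would also persist. The brain-metastasis subgroup in SAP 5.2.4 is conditional and not defined by prior CNS treatment. SAP 5.1 tabulates A1 and A2 separately, which helps, but also gives a pooled Part A.

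**4. The plan's own figures.** None is stated for icORR. The named interval method was checked on Protocol Table 16. With x responses in n patients, the Clopper–Pearson 95% limits are the 0.025 quantile of Beta(x, n−x+1) and the 0.975 quantile of Beta(x+1, n−x). Results: 35/100 gives 25.7–45.2%, 40/100 gives 30.3–50.3%, 45/100 gives 35.0–55.3%. All match.

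**5. Scale, under assumptions only.**

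- From the documents: Part B has 40 patients, 20 per cohort (SAP 3.3).
- Assumed share with CNS lesions at entry: 25–40%. Protocol 2.1.2 gives this as the share of NSCLC patients who develop brain metastases, which is not the same thing. Per cohort: 20 × 0.25 = 5 to 20 × 0.40 = 8. Part B: 10 to 16.
- Effect of one response: 1/8 = 12.5 points to 1/5 = 20 points among CNS patients; 1/20 = 5 points if all treated patients are the denominator.
- Further assumptions, with no source in the documents: no drug effect in the CNS; 25–75% of CNS patients locally treated and not progressing; 20–40% of those meeting response criteria from local treatment alone.

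| Case (Part B) | Responses | CNS denominator (95% CI) | All-treated denominator (95% CI) |
|---|---|---|---|
| Low: 10 × 0.25 ≈ 2; 2 × 0.20 = 0.4 | 0 | 0/10 = 0% (0–30.8%) | 0/40 = 0% (0–8.8%) |
| High: 16 × 0.75 = 12; 12 × 0.40 = 4.8 | 5 | 5/16 = 31.25% (11.0–58.7%) | 5/40 = 12.5% (4.2–26.8%) |

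Under the same assumptions, the patients with an untreated or since-progressed lesion would number from 10 − 8 = 2 (10 × 0.75 = 7.5, taken as 8) to 16 − 4 = 12. With no responses among them, the upper 95% limit is 84.2% for 0/2 and 26.5% for 0/12.

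**The case against.** A reader might infer that the plan counts shrinkage of recently irradiated brain lesions as drug response. The documents do not say that. They are silent and defer to RECIST v1.1 and, for Parts B and C, to a Site Imaging Manual with central response assessment (Protocol 7.1.1). Either could restrict which CNS lesions qualify, and neither is supplied. This part of the objection stands. It does not close the gap: the manual is not cited for Part A, where the investigator's icORR is reported, and the SAP's pointer to protocol Appendix C for response confirmation leads nowhere, since the current protocol has only Appendix A.

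A reader might also take the 2-week and 7-day washouts to mean that freshly irradiated lesions enter freely. The 4-week stability and off-steroid conditions apply as well, and Part A1 counts its 4 weeks from CNS-directed treatment, so the route is narrower.

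An inflated icORR could be projected from assumed drug and radiation response rates, but the result would only restate the assumptions. The documents give neither rate, nor the share of patients with prior brain radiotherapy.

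The remaining objections are practical. icORR is descriptive, no decision threshold uses it, there is no formal hypothesis, and the protocol does not list it as a Part A endpoint. Restricting icORR to unirradiated or progressed lesions could leave almost nobody. The SAP 5.3.3 items are listed as yes/no characteristics, and the progression item does not say whether the last treatment was local or systemic. These points argue for a split that keeps the overall estimate, rather than a restriction. They do not justify leaving the two kinds of patient mixed.

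**Conclusion.** The point holds as a gap in attribution. Nothing in Table 15 or SAP 5.5.4–5.5.5 excludes or separates locally treated, non-progressing CNS lesions. In Part A1 the known baseline lesions are of that kind by eligibility, and in Parts A2, B and C they may be. Unless RECIST v1.1 or the imaging manual settles the matter, a CNS response in these patients cannot be read as the effect of TAS3351 alone. The pooled Part A icORR is therefore weak support for a brain-metastasis cohort.

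The size of any bias cannot be derived from the documents. The illustration shows only that the estimate is fragile at these numbers. Its larger figures need a CNS-disease denominator, which the SAP does not state. The primary endpoint is untouched. The change is still worth making before results are seen, because it alters what the trial can conclude about brain activity.

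**What to change.** In SAP 5.5.4 and 5.5.5, for investigator and ICR assessment where each applies:

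- Keep overall icORR and icDoR, with patients who have baseline CNS lesions as the stated denominator.
- Also tabulate both in two groups: (a) patients with at least one baseline CNS lesion that had no prior local treatment or progressed after it; (b) patients whose CNS lesions were all locally treated and not progressing.
- Base any claim of CNS activity on group (a).
- Derive the groups from the SAP 5.3.3 CNS variables together with the prior radiotherapy and surgery data, and state whether the 5.3.3 progression item refers to local treatment.
- Show Part A1 separately from A2 in these tables.
- Apply the same split to Part C through Protocol Table 15 or the Part C SAP. If RECIST v1.1 or the Site Imaging Manual already sets a lesion rule, cite it.

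Cost: SAP wording, an added tabulation, and some derivation work, because the 5.3.3 items are listed as yes/no per patient and brain-field radiotherapy is not among the summarised variables. The groups will be small and the intervals wide. A patient with both treated and untreated lesions stays in group (a), so the split reduces the ambiguity without removing it.

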5.5.5. Intracranial DoR (icDoR)

Both icDoR by ICR and icDoR by investigator will be performed.

Event and censoring rule are the same with DoR event and censoring rule.

Secondary Analysis in Part A & B – icDoR by investigator

- The Kaplan-Meier method will be used to estimate the median and percentile with the 2-sided 95% CI calculated using the Brookmeyer and Crowley method.
- Swimmer plot of treatment duration and response will be provided.

Secondary Analysis in Part B – icDoR by ICR

- The Kaplan-Meier method will be used to estimate the median and percentile with the 2-sided 95% CI calculated using the Brookmeyer and Crowley method.
- Swimmer plot of treatment duration and response will be provided.

5.5.6. Progressive Free Survival (PFS)

Table 6: Event and Censoring Rules for PFS

Event/Censor	Decision	Date of event or censor to consider for analysis
Documented first disease progression	Event	Date of 1st PD scan
Death without disease progression	Event	Date of Death
Patients who not known to have progressed or died at the time of data cut-off	Censor	Date of last evaluable tumor scan (non-NE)
Patient progresses or dies immediately after two or more consecutive missed visits	Censor	Date of last evaluable tumor scan prior to the two missed visits (non-NE)
No baseline or post-baseline tumor assessment unless they die within two visits of baseline (<12 weeks from baseline)	Censor	Date of the first dose

For missing data, i.e., patients who were not known to have progressed or died at the time of data cut-off or who were progressed or died after 2 or more consecutive missed visit, the PFS will be censored at the date of last evaluable tumor scan. If no tumor assessments are performed unless patients die within two visits of baseline visit, PFS will be censored at the time of the first administration.

Secondary Analysis in Part A (Patients in part A2 only), B

The Kaplan-Meier method will be used to estimate the median and percentile with the 2-sided 95% CI calculated using the Brookmeyer and Crowley method.

Kaplan-Meier plot will be provided.

